9.2 ATTRIBUTION OF ADVERSE EVENTS.....	13
9.3 ADVERSE EVENT REPORTING.....	13
10 STATISTICAL PLAN	13
10.1 DATA ANALYSIS, SAMPLE SIZE, AND PRECISION	13
11 DATA COLLECTION, HANDLING AND STORAGE	14
12 STUDY MANAGEMENT PLAN	15
12.1 STUDY COORDINATION.....	15
12.2 PERFORMANCE MONITORING:	15
12.3 DATA AUDITS:	15
12.4 DATA EDITS:	15
APPENDIX: STUDY VARIABLES	17

[figure not shown]
Abstract

Nursing homes are settings with a high rate of *Staphylococcus aureus* (SA) acquisition, which leads to infection, particularly for short stay residents. The current standard of care for preventing SA acquisition and SA infection in nursing homes is Standard Precautions (gowns and gloves for *anticipated* contact with blood, body fluids, skin breakdown or mucous membranes) for all residents.

We propose a feasibility study of a novel strategy, the *addition* of targeted gown and glove use, to prevent SA acquisition and SA infection in residents of community-based nursing homes. Our novel strategy is based on prior research on the risk of transmission from residents to healthcare workers' (HCWs) gowns and gloves, the first step in SA transmission. Rather than wearing gowns and gloves for all care activities to prevent transmission (as in Contact Precautions), gown and glove use can be targeted to specific high risk "moments" of care for specific high risk residents. High risk "moments" for gown and glove use are care activities most likely to transmit SA to HCW clothing and hands (in the absence of gown and glove use) based on prior research. (1, 2) Residents with chronic wounds and medical devices are: 1) most likely to be colonized with SA; 2) most likely to acquire SA; 3) most likely to transmit SA to HCW clothing and hands; and 4) most likely to develop a SA infection based on prior research (1-3) and thus would be considered high risk residents.

We will perform a quasi-experimental (before-after) study of this intervention, targeted gown and glove use, at two community-based nursing homes to demonstrate its feasibility and evaluate its effect on SA acquisition and SA infection rates. A quasi-experimental study design allows each nursing home to act as its own control, reducing variability. During a two month baseline period, we will measure SA acquisition and SA infection using surveillance cultures from residents and review of health care records. We will also assess gown and glove use for high risk care in high risk residents during the baseline period and begin to develop the intervention using a participatory human factor engineering informed approach. During a one month training period, we will begin phase implementation of the intervention in the nursing homes. During a two month intervention period, we will again measure SA acquisition and SA infection using surveillance cultures from residents and review of a state-wide electronic health information repository. We will also assess gown and glove use for high risk care in high risk residents during the intervention period and evaluate the intervention. SA acquisition is an excellent measure of resident-to-resident SA transmission, which our intervention is designed to decrease. It is also a more frequent outcome than SA infection, increasing the power of our study to detect a difference if one exists. We will assess adherence with all components of the intervention and the change in gown and glove use between baseline and intervention periods.

Figure 1. Overview of Project

1 Background

1.1 *Rationale*

Nursing homes are healthcare settings that house a high prevalence of people with both MRSA and MSSA colonization, creating a high risk for resident-to-resident transmission of *Staphylococcus aureus* (SA). There is a mingling of long term and short term stay residents in community-based nursing homes which mix a population recovering from acute illness with a chronically ill population which has high prevalence of SA colonization. For example, we found that short stay residents are at four-fold higher risk for MRSA acquisition than long stay residents. Once SA acquisition occurs, people are at higher risk for infection as colonization typically precedes infection. Up to 30% of MRSA colonized patients develop an infection contributing to community onset invasive SA infections. Nursing home stay was identified as a common risk factor for invasive MRSA infection after recent hospital discharge.

Nursing home staff are the most frequent vector for SA transmission as their clothing and hands become contaminated with SA during the care of SA colonized residents. In contrast to hospitals, where the standard of care for patients with MRSA is Contact Precautions (gowns and gloves for all patient contact), community-based nursing homes typically use Standard Precautions (gowns and gloves for anticipated contact with blood, body fluids, skin breakdown or mucous membranes) for residents with MRSA. Prior research demonstrating high rates of MRSA acquisition in nursing homes suggests that Standard Precautions do not adequately reduce the transmission of SA.

Contact Precautions have not been widely adopted by nursing homes for several reasons. Nursing homes are resource-limited settings without the level of professional staff and laboratory infrastructure of hospitals. In addition, nursing home staff have deeply rooted beliefs that Contact Precautions stigmatize residents. There is a clear need for a solution - tailored to the nursing home setting - to reduce the risk of SA (and other antibiotic resistant bacteria) acquisition and infection. Our goal in this project is to demonstrate the feasibility of a novel intervention, targeted gown and glove use, to decrease SA acquisition and SA infection as a precursor for a future multisite stepped wedge cluster trial.

1.2 *Population*

Study participants will be nursing home (NH) residents and staff in participating community-based NH study sites. All study activities will occur in the participating community-based NH study sites.

1.3 *Risk/Benefits*

The risks related to this study are minimal – the same as that encountered in daily life or at a routine doctor's visit. There are two types of participants, NH residents and staff. The two types of participants have different risks which we have minimized.

Potential risks to resident participants include those associated with non-invasive cultures (anterior nares and inguinal fold skin) and the loss of confidentiality of individual health information collected as part of the study.

We will minimize these risks as follows. Resident participants will be educated on how the cultures are performed at the time of enrollment to reduce any psychological discomfort. Study coordinators will have competencies in doing these procedures and will use gentle pressure to reduce possible irritation or discomfort during from the culture procedures.

Access to study records will be restricted to study staff, investigators and officials of the Office of Human Research Protections. Every effort will be made to keep the study records confidential through the use of locked briefcases for transport of paper records, assignments of unique participant identifiers, password protected databases and storage of paper records in locked filing cabinets in rooms that are locked when not in use (see **11. Data Handling and Record Keeping** for additional details).

There are few, if any potential risks to staff. Staff will be observed during routine care in order to estimate gown and glove use. A number of staff will be shadowed in order to determine how to best implement the intervention, targeted gown and glove use. A few staff will serve as liaisons to the project team. All staff will wear disposable gowns and non-latex gloves while providing specific care for specific residents during the intervention period. Wearing gowns and gloves are part of Standard (infection control) Precautions for certain care activities and pose no risk to the staff. We will not collect any identifiable data on any staff and thus there is no risk of loss of confidentiality.

Preventing the Spread of Infection in Nursing Homes

There is no direct, individual benefit that can be guaranteed as a result of participation in this research study. There is societal benefit as this study will provide information about the transmission of *S. aureus* and other bacteria that could ultimately reduce the risk of infection for other nursing home residents. All residents and staff will be given the opportunity to have their questions answered by the study coordinators or investigators as needed. Given the minimal risks to the participants, the benefits outweigh the risks.

1.4 Study Conduct

This study will be conducted in compliance with the current protocol approved by the Institutional Review Board and according to Good Clinical Practice standards. All study documents will be posted on a secure document management site. No deviation from the protocol will be knowingly implemented without the prior review and approval of the IRB except where it may be necessary to eliminate an immediate hazard to a research subject. In such case, the deviation will be reported to the IRB as soon as possible.

2 Study Objective

Our goal in this project is to demonstrate the feasibility of a novel intervention, targeted gown and glove use, to decrease SA acquisition and SA infection as a precursor for a future multisite stepped wedge cluster trial. Our targeted intervention limits both cost and stigma while blocking the transmission and acquisition of multiple organisms.

Objective 1: To implement a targeted gown and glove intervention in two community-based nursing homes.

Expected Outcome 1: A targeted gown and glove intervention can be successfully implemented across two community-based nursing homes with >80% compliance with gown and glove use for high risk care in high risk residents.

Objective 2: To evaluate the impact of a targeted gown and glove intervention on SA acquisition and SA infection rates.

Expected Outcome 2a: The intervention will decrease SA acquisition and infection rates.

Expected Outcome 2b: We will determine the effect size to guide the design (including the sample size) of a future trial.

Objective 3: To develop an implementation “toolkit” that can be easily adapted and implemented at nursing homes in a future trial.

Expected Outcome 3: Barriers to and strategies for implementation of the targeted gown and glove intervention will be identified leading to modification of the pilot intervention and development of an implementation “toolkit” for a future trial.

3 Study Design

3.1 Primary Study Endpoints/Secondary Endpoints

Outcome 1: Compliance with each component of the intervention (identification and flagging of high risk residents, use of gowns and gloves for high risk care) based on 1) weekly point prevalence studies for high risk residents and 2) weekly observations of high risk care interactions with 5-10 residents over the 2-month intervention periods. There will also be weekly observations of high risk care interaction of 5-10 residents over the 2-month baseline period to assess the change in gown and glove use.

Outcome 2a: The primary outcome will be a change in SA acquisition rates comparing baseline and intervention periods. Residents in the nursing home will be swabbed at the start of the study period, or when they are admitted. Then they will all be re-swabbed at discharge or when the study ends. Acquisition will be defined as a positive culture for a new SA in a resident who was negative for that SA at the start of the study period or admission. Cultures will be performed in the research lab using well established methods. Specimens will be saved for future evaluation of other bacteria. The secondary outcome will be invasive SA infections and other infections within 90 days of nursing home admission in residents as detected through surveillance from health care records including but not limited to CRISP, a state-wide central repository of health care records including hospital and nursing home discharge summaries.

Outcome 2b: The observed SA acquisition rate reduction from this pilot study will be used to estimate the effect size that will inform the sample size for a larger trial.

Outcome 3: We will qualitatively examine the acceptability of, and any barriers to implementation using broad stakeholder feedback. Elements found to be infeasible or unacceptable will be modified at each stage and an implementation toolkit will be developed for the future trial.

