Confidentiality will be maintained to the fullest extent permitted by law. All study data collected at the NHs will be recorded on case report forms. These case report forms will be entered into a password protected relational database which will be kept on a research server which has a level and scope of security that equals or exceeds that established by the HIPAA Security Rules. Clinical data on study participants will be obtained electronically from the participating NHs and uploaded into the study database. Data regarding *S. aureus* infections will be sourced from a state-wide electronic health information repository and entered into the study database. Paper records will be stored in locked filing cabinets in a protected space. Data will be maintained on a secure electronic central database on a research server. Data will be backed up according to the network backup schedule.

A unique identifier or code will be assigned to each resident participant. Bacterial isolates and culture specimens and datasets used for analysis will be labeled with this code. Only the study personnel who directly interact with subject or manage the subject's clinical protocol data will have access to participant identifying information. Culture data will be entered directly into the relational database; however, microbiology laboratory personnel will not have access to participant identifiers in the database. Study personnel who leave the research team will have their access to study data removed.

As soon as permitted and when all data analyses are complete and have been published, source documents containing identifiable information will be shredded and identifying information will be removed from the database. During the entire study, all data will be managed centrally at the primary site. There will be a single data table which maintains the link between the unique code and patient identifiers. This table containing the link between code and identifying information will be destroyed on the server and in any backups when it is time to de-identify the database. If any paper copies of the link have been made, they will be shredded. PHI will not be shared or disclosed unless required by law.

B. *Research could not practicably be conducted without the waiver or alteration*

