Serious Adverse Events that are more likely than not (probably or definitely) related to the research will be reported immediately of the site investigator becoming aware of the SAE to the local IRB according to established IRB policy. The principal investigator will evaluate the adverse event and determine whether the adverse event affects the Risk/Benefit ratio of the study and whether modification to the protocol is required.

The principal investigator will conduct a review of all serious adverse events annually. The principal investigator will evaluate the frequency and severity of the serious adverse events and determine if modifications to the protocol is required. A summary of the serious adverse events will be reported to the UMB IRB annually, when renewal is sought.

10 **Statistical Plan**

10.1 **Data Analysis, Sample Size, and Precision**

For objective 1, we will calculate point estimates and 95% confidence intervals for the rates of compliance with each component of the intervention (identification and flagging of high risk residents, use of gowns and gloves for high risk care) as well as the change in gown and glove use for high risk care during the baseline and intervention periods. We will observe 40-80 encounters per nursing home where gowns and glove should be used which will result an estimate of the rate of compliance that is accurate +/- 8-10 percentage points.

For objective 2, we will estimate and compare the rates of transmission in the baseline and intervention periods in each nursing home. To estimate the rates from binary data, we note that the risk that a person acquires the infection in the interval between swabs can be written as $1-\exp(-\lambda t)$ where “ t ” is the number of days between swabs and λ is interpretable as the daily rate of acquisition. We will estimate λ in the baseline and intervention periods using maximum likelihood estimation and compare the two rates. Likelihood methods will be used to calculate a confidence interval for the ratio of the rates. This will be done for each nursing home separately. We will test 100 residents per nursing home per period which will result in an estimate of the rate of acquisition that is accurate +/- 4-6 percentage points. These estimates will give us insight into the effect size of the intervention and the variation between nursing homes for future planning.

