Proportion of Beds- Rehab or Skilled nursing	Facility Start-up	Administrator	Descriptive	Ratio
Proportion of Beds- Short stay	Facility Start-up	Administrator	Descriptive	Ratio
Resident to staff ratio by Type of HCW and Shift	Facility Start-up	Administrator	Descriptive	Ratio
Staff Infection Control Training	Facility Start-up	Administrator	Descriptive	Yes/no; record policy
Full time employees for Infection Prevention in Facility	Facility Start-up	Administrator	Descriptive	Interval
OUTCOME VARIABLES				
SA or other Infection	Within 90 days of at admission or study period start	MR	Outcome variable	Yes/no
SA colonization of Anterior nares	At admission or study period start/discharge or study period end	Culture	Outcome variable	Yes/no
SA colonization of Inguinal skin	At admission or study period start/discharge or study period end	Culture	Outcome variable	Yes/no
STAFF/HCW OBSERVATIONS (weekly for 5-10 high risk care activities in each nursing home during both the baseline period and the intervention period)				
Gown use	Observation visits	Observation	Study variable	Yes/no
Glove use	Observation visits	Observation	Study variable	Yes/no

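### Does the missing rule for a new S. aureus, and the unnamed at-risk set behind the ±4-6 point precision, require a change to the primary acquisition analysis?

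*Combined protocol and SAP*

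**What the plan says.** Section 3.1 makes the change in SA acquisition rate the primary outcome and defines the event as "Acquisition will be defined as a positive culture for a new SA in a resident who was negative for that SA at the start" (or on admission). Two body sites, anterior nares and inguinal skin, are swabbed at entry and again at exit (sections 8.1 to 8.3). The Appendix lists one outcome variable for each site, for example "SA colonization of Anterior nares", in yes/no format. Section 3.1 also notes: "Specimens will be saved for future evaluation of other bacteria". Section 6.3, repeated in section 11, states: "Bacterial isolates and culture specimens and datasets used for analysis will be labeled with this code".

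Section 10.1 models "the risk that a person acquires the infection in the interval between swabs" as 1 − exp(−λt), estimates λ by maximum likelihood in each home and period, and compares the two periods through the ratio of rates. On size it says "We will test 100 residents per nursing home per period", giving "an estimate of the rate of acquisition that is accurate +/- 4-6 percentage points". Section 1.1 says that nursing homes "house a high prevalence of people with both MRSA and MSSA colonization", without a figure. Outcome 2b uses the observed reduction to size a later trial.

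**The concern.** The definition compares one SA with another, but the listed data record only whether SA grew. On those variables alone, a resident positive at both swabs could be a persistent carrier or a new acquisition. No rule says what separates two SA (MRSA against MSSA, or strain) or how the two sites combine into one result per resident.

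Section 10.1 does not repeat the at-risk condition. One analyst might drop first-swab carriers, another keep them as non-events, and a third keep them at risk for a different SA. The precision statement gives no acquisition risk and no allowance for carriers.

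At stake are the level of the primary outcome and the effect size passed to the next trial. Counting carriers as at risk while never letting them have an event would pull the acquisition rate down.

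**Working it through.** **Inputs.** From section 10.1: 100 residents per home per period, ±4-6 points, the model 1 − exp(−λt). The documents give no acquisition risk, no carriage figure and no confidence level for objective 2. Assumed here: 95% two-sided intervals, acquisition risk p of 5-10%, first-swab carriage c of 30-50%, and 70-80% of carriers positive again at the second swab. Carriers are taken to face the same risk of a different SA as non-carriers.

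**1. The plan's own precision.** Half-width = 1.96 × √(p(1 − p)/n).

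- n = 100, p = 5%: 1.96 × √(0.05 × 0.95/100) = 4.3 points.
- n = 100, p = 10%: 1.96 × √(0.10 × 0.90/100) = 5.9 points.
- Solved backwards at n = 100, ±4 needs p of about 4.4% and ±6 about 10.5%.

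So ±4-6 is what 100 residents at risk would give at plausible risks.

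**2. Precision if only SA-negative residents are at risk.**

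| At risk | p = 5% | p = 10% | Risks that give ±4 and ±6 |
|---|---|---|---|
| 100 | 4.3 | 5.9 | 4.4%, 10.5% |
| 70 (30% carriage) | 5.1 | 7.0 | 3.0%, 7.1% |
| 50 (50% carriage) | 6.0 | 8.3 | 2.1%, 4.9% |

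The figure may be somewhat optimistic under this reading, but lower risks reproduce it. Nothing in the documents excludes either case.

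**3. How many residents are affected.** Positive at both swabs per 100 = 100 × c × proportion positive again: 21-24 at 30% carriage, 35-40 at 50%.

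**4. Effect on the planned comparison.** Take a true fall from 10% to 5% and keep every carrier as a non-event, so that observed risk = (1 − c)p. The rate ratio is log(1 − observed risk, intervention)/log(1 − observed risk, baseline).

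- c = 0: log(0.95)/log(0.90) = 0.487.
- c = 30%: log(0.965)/log(0.93) = 0.491.
- c = 50%: log(0.975)/log(0.95) = 0.494.

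For scale, 10 against 5 events in one home gives a standard error of the log ratio of about √(1/10 + 1/5) = 0.548. The 95% interval is 0.487 × exp(±1.96 × 0.548), or about 0.17 to 1.4. A shift of 0.007 is invisible against that.

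**5. Effect on the absolute reduction.** With carriers kept as non-events, the 5-point fall becomes 0.7 × 5 = 3.5 or 0.5 × 5 = 2.5 points. If carriers enter only when the second swab is negative (a fraction q of 20-30% of them), the fall is (1 − c) × 5/((1 − c) + cq): 4.4-4.6 points at 30% carriage and 3.8-4.2 at 50%.

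**6. Is the missing field evidence of missing data?** The Appendix has no swab date, although section 10.1 needs the days between swabs. It also omits recent antibiotic use and recent hospitalization, which section 6.3 says will be collected, and serious adverse events, which section 9.1 collects. It is not a full inventory, so the lack of an isolate-type field says little. Section 6.3 names isolates separately from specimens and ties both to the resident code, so a comparison is open to the laboratory. That specimens are stored for other organisms does not bear on this.

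**The case for a change.** The strongest case for a change is that this is the primary outcome, and that a comparison being possible is not the same as its being planned. No matching rule, resident-level rule across sites or result field is written. The stable ratio also depends on stable carriage, which a before-after design with separate two-month periods does not guarantee. With no true effect, a 10% risk and carriers kept as non-events, a rise in carriage from 30% to 40% alone gives log(0.94)/log(0.93) = 0.85.

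The omission stands as a fact, and so does the lack of a stated risk behind the precision. The 0.85, however, needs both an assumed shift in carriage and a handling at odds with section 3.1. That definition counts a resident as at risk only for an SA not already carried, so it requires a comparison before a both-positive resident is scored. Scoring all such residents as non-events without one departs from the plan. Section 10.1 models whether a person acquires SA, and in a single combined document that term takes its meaning from section 3.1.

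**Conclusion.** No change follows. This is missing detail that the analysts can fill from what the plan already has: the definition in section 3.1, coded isolates, and, from the listed variables alone, the residents negative at both sites at the first swab. No stated rule gives a wrong result, and ±4-6 points is unsupported rather than wrong.

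For the planned rate ratio the effect is 0.487 against 0.491-0.494, given stable carriage. For the absolute reduction it ranges from about half a point to 2.5 points out of 5, and arises only if the definition is set aside. A later trial using the same definition and denominator would also want the rate measured that way. All of these sizes rest on assumed carriage, acquisition risk and persistence.

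Nor is either remedy a clear gain. Typing isolates may need laboratory work that the documents do not describe, and an MRSA/MSSA split would still miss a new strain of the same type. Restricting to SA-negative residents narrows the endpoint, and having 100 at risk would mean swabbing 100/0.7 = 143 to 100/0.5 = 200 residents per home per period. In a two-home feasibility study with no power claim, that choice is a fair trade-off to leave with the investigators.

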3.3 Duration

Each of two nursing homes will participate for a period of approximately 6 months. After an initial month of engagement, the next 2 months will be a baseline data collection period; the next 1 month, an intervention training period and the final 2 months, an intervention data collection period.

4 Selection and Withdrawal of Participants

All residents present in the two nursing homes during the project will be potential participants. HCWs can participate in a number of ways. HCWs will be observed during routine care in order to estimate gown and glove use. A number of HCWs will be shadowed in order to determine how to best implement the intervention, targeted gown and glove use. Up to 6 HCWs will serve as liaisons to the project team. All HCW will wear disposable gowns and non-latex gloves while providing specific care for specific residents during the intervention period.

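### The pilot cannot estimate the reduction in SA acquisition precisely enough to serve as the future trial's planning effect, even with both homes pooled, and section 10.1 gives no precision for the rate ratio

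*Combined protocol and SAP*

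**What the plan says.** Section 2 (Study Objective), Expected Outcome 2b: "We will determine the effect size to guide the design (including the sample size) of a future trial". Section 3.1, under the outcome with the same number, applies this to a larger trial and reads "The observed SA acquisition rate reduction from this pilot study will be used to estimate the effect size that will inform the sample size". Section 10.1 is milder: "These estimates will give us insight into the effect size of the intervention and the variation between nursing homes for future planning".

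On study size, section 10.1 says "We will test 100 residents per nursing home per period", which is expected to give "an estimate of the rate of acquisition that is accurate +/- 4-6 percentage points". That is the precision of one proportion, in one home, in one period. For the comparison of periods it says "Likelihood methods will be used to calculate a confidence interval for the ratio of the rates", for each home on its own, without saying how wide that interval should be.

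The documents give no baseline acquisition rate, no target or minimum worthwhile reduction, and no other input to the future sample size. They do not say how the interval would enter the sizing. Section 3.2 makes each home its own before-after control, with no concurrent comparison.

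**The concern.** Supplying an effect size for the later stepped-wedge trial is a stated outcome under Objective 2. The only precision offered, +/- 4-6 points, looks tolerable until one notices that it describes a single proportion. The planning quantity is a ratio of two such estimates, each resting on few acquisitions. If that ratio is largely sampling error, a chance large reduction leads to a follow-on trial that is much too small, and a chance small one to a trial that is much too large. Pooling the two homes, which section 10.1 does not plan, is the most favourable case for the design, so it is the case tested here.

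**Working it through.** **Inputs.** From the documents: 100 residents per home per period (section 10.1), two homes (section 2, Objective 1), and risk = 1-exp(-λt) (section 10.1). Assumptions: all 100 residents are evaluable, follow-up is equal in the two periods, baseline risk is 5-10% per interval, and the true rate ratio is 0.5 or 0.7. The future trial's error rates are not stated; two-sided 5% and 80% power are assumed.

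**1. The plan's own figure.** The half-width is 1.96·√[p(1-p)/100].
- p = 5%: 1.96·√(0.0475/100) = 4.3 points.
- p = 10%: 1.96·√(0.09/100) = 5.9 points.

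Solving for exactly 4 and 6 points gives p = 4.35% and 10.5%. The stated precision is reproduced, and it implies a baseline risk of roughly 4-10%. This shows consistency; it does not confirm the rate independently.

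**2. Precision of the rate ratio.** With equal follow-up, λ = -ln(1-p)/t, so the intervention-period risk is p1 = 1-(1-p0)^RR. Then Var(log λ̂) = p/[(1-p)·n·ln(1-p)²], and SE(log RR) is the square root of the sum over the two periods.

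Worked case: both homes (n = 200 per period), p0 = 10%, RR = 0.5.
- p1 = 1-0.9^0.5 = 5.13%.
- The variances are 0.0500 and 0.0975, so SE = √0.1475 = 0.384.
- CI = 0.5·exp(±1.96·0.384) = 0.24 to 1.06.

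| Homes | Baseline risk | True ratio | Expected acquisitions (baseline, intervention) | SE(log RR) | Expected 95% CI |
|---|---|---|---|---|---|
| Both | 10% | 0.5 | 20, 10.3 | 0.384 | 0.24-1.06 |
| Both | 10% | 0.7 | 20, 14.2 | 0.347 | 0.35-1.38 |
| Both | 5% | 0.5 | 10, 5.1 | 0.545 | 0.17-1.46 |
| One | 10% | 0.5 | 10, 5.1 | 0.543 | 0.17-1.45 |

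Even the narrowest interval runs from a 76% reduction to a 6% increase.

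**3. What this does to sizing (illustration only).** Suppose the observed proportions were put into n per arm = (1.96+0.84)²·[p0(1-p0)+p1(1-p1)]/(p0-p1)². This has no clustering and no stepped-wedge design effect. At 10% and a true halving, the bracket is 0.0900+0.0487 = 0.1387 and the squared difference is 0.0487² = 0.00237, so the formula gives about 459 at the true values. True power falls below 50% when n is under 1.96²·0.1387/0.00237, about 225. Simulating pilots with 200 residents per period (simple binomial counts) gives:

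| Baseline risk | True ratio | Pilots showing no reduction | Of those showing a reduction, implied trial has true power below 50% |
|---|---|---|---|
| 10% | 0.5 | 4% | 22% |
| 5% | 0.5 | 12% | 32% |
| 10% | 0.7 | 17% | 40% |

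**4. Sensitivity.** Over the whole back-solved range (4.35-10.5% baseline, true reductions of 30-50%), the pooled interval runs from 0.25-1.97 at worst to 0.24-1.04 at best, so it always includes 1. The share below 50% power is 21-55%. At 20% baseline, outside what the stated precision implies, a true halving gives 0.29-0.85 with 13% below 50% power. A 30% reduction still gives 0.43-1.13 with 29% below.

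**The case against.** The strongest reply is that the plan fixes no rule. Its verbs are to inform, to guide and to give insight. A reader might infer that the observed point estimate will be the sole, mechanical input to the next sample size, but no formula or sole-input statement supports that. This stands, so the simulation shows one possible use and not what the plan prescribes. It does not dispose of the point, because Expected Outcome 2b still says the effect size will be determined here, and no other input is named.

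Three further inferences should be resisted.
- A reader might infer that a chance null result would end the programme. The documents contain no progression rule tied to acquisition.
- A reader might take the share of implied trials below 80% power, about half, as the measure of harm. It is not: a nearly unbiased planning estimate falls short about half the time at any pilot size. At 10% baseline and a true halving, the share is 53% with 200 residents per period and still 50% with 2,000. The share below 50% power does respond to precision, falling from 22% to under 1%.
- A reader might take 459 per arm as the right size for the next trial. That trial is a stepped-wedge cluster design, whose size also depends on clusters, steps and intracluster correlation.

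It is also fair that a CI for the ratio is already planned, that the later trial will need its own sample-size justification, and that nothing here alters this study's procedures or participant risk.

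**Conclusion.** The point holds in this form: the design cannot deliver the effect size that Expected Outcome 2b and Outcome 2b promise, and section 10.1 does not show the reader this because it gives no precision for the ratio. At baseline risks consistent with the plan's own +/- 4-6 points, the pooled interval is compatible with anything from a very large reduction to an increase. It is wider still in the planned home-by-home analysis.

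The size of the problem rests on assumed baseline risks and true reductions, since the documents state neither, and on every tested resident being evaluable. The calculation leaves out clustering, missed second swabs and residents who contribute to both periods. Within-resident correlation might help a little; the others would mostly widen the interval. Secular change between periods would add bias that more residents cannot remove. This does not invalidate the pilot, but it undermines one of its stated purposes and should be corrected.

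**What to change.** Reword three places: Expected Outcome 2b (section 2), Outcome 2b (section 3.1) and section 10.1.
- State that the future trial will be sized on a minimum worthwhile reduction set in advance.
- State what the pilot supplies to that calculation: the baseline daily acquisition rate, the fraction of residents at risk of a countable acquisition, completeness of the second swab, and compliance.
- Report the observed rate ratio with its CI as a plausibility check on the chosen target, not as the planning effect.
- In section 10.1, give the expected precision of that ratio, with the assumed baseline rate, beside the existing +/- 4-6 points.
- Say that two homes give little information on between-home variation, so that input must come largely from elsewhere.

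Data collection does not change. The cost is more than editorial in one respect: Expected Outcome 2b becomes narrower. The target reduction must be justified on other grounds, and the pilot's effect estimate carries less weight.
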